5.3 Concomitant Therapy

All supportive measures consistent with optimal subject care will be given throughout the study. Concomitant medications will be captured in the CRF beginning at screening. Packed red blood cell or platelet transfusions are allowed when necessary. Growth factor use (including erythropoietin) is not allowed with the exception of the use of filgrastim (G-CSF) or pegfilgrastim, which is permitted ONLY when used to treat febrile neutropenia or in patients who have prolonged (one week or more) grade 3-4 neutropenia, after approval from Principal Investigator. Concomitant use of cytotoxic chemotherapeutic agents (e.g. hydroxyurea), or other experimental drug or therapy for myelofibrosis while the subject is on study is prohibited. Concurrent use of strong inducers or strong inhibitors of CYP3A4 (strong inducers are rifampin and St. John's Wort; strong inhibitors are HIV-antivirals, clarithromycin, itraconazole, ketoconazole, nefazodone, and telithromycin) is prohibited.

Lenalidomide increases the risk of thrombotic events in patients who are at high risk or with a history of thrombosis, in particular when combined with other drugs known to cause thrombosis. When lenalidomide is combined with other agents such as steroids (e.g. dexamethasone, prednisone), anthracyclines (Doxil, adriamycin) and erythropoietin the risk of thrombosis is increased. Consideration should be given to the use of aspirin (81 or 100 mg) as prophylaxis as deemed appropriate (through commercial supply, not provided by the Incyte or Celgene companies). When the platelet count falls below $35 \times 10^9/L$, aspirin prophylaxis should be discontinued until the platelet count is $> 35 \times 10^9/L$ and stable (not less than prior measurement) or increasing on two consecutive measurements at least 4 days apart.

5.4 Pharmacokinetic Assessment

Blood samples will be collected for pharmacokinetic (PK) analysis at three different time points. Patient medical number will be changed to a code that could only be deciphered by the principal investigator, thus preserving patient confidentiality. This collection will involve an additional procedure (a needle stick) at these time points. Time of the dose taking and PK sample draw time will be recorded in the draw sheets that are part of patients' medical records. Blood samples will be centrifuged to obtain plasma and stored at $-20^{\circ} C$ until shipment to Incyte Corp., who will perform the testing.

5.5 Pretreatment Evaluation

- History and physical exam including vital signs, body weight and height, and spleen and liver measurements. This also includes a transfusion history for 3 months prior to day 1 and concomitant medication notation (within 14 days of study day 1)

- CBC and differential, electrolytes (Na, K, Cl HCO₃), creatinine, uric acid, BUN, glucose, total bilirubin, and SGPT, PT/PTT, INR (within 14 days of study day 1).
- Bone marrow biopsy and aspirate (within 3 months of study day 1) with cytogenetics (if not done before) and JAK2V617F status and allele burden.
- Urinalysis (within 14 days of study day 1)
- ECG (within 14 days of study day 1)
- Pregnancy test (for FCBP only) with a sensitivity of at least 50 mIU/mL, within 10 – 14 days prior to and again within 24 hours of starting lenalidomide.
- Myelofibrosis Symptom Assessment Form (MFSAF) questionnaire and MDASI (MD Anderson Symptom Inventory) questionnaire (within 3 days of study day 1)

5.6 Evaluation During Study

- Directed history and physical examination including vital signs, body weight, and spleen and liver measurements prior to each cycle for the first 3 cycles then every 3 to 6 cycles. This also includes a transfusion history for previous cycle of therapy and concomitant medication notation.
- CBC and differential, electrolytes (Na, K, Cl HCO₃), creatinine, BUN, glucose, total bilirubin, and SGPT weekly for 2 cycles, then every 2 weeks while on therapy. Those responding patients continuing therapy past 6 cycles and on a stable dose level without interruption or delay for 4 cycles may have blood tests done monthly)
- Bone marrow aspiration with cytogenetics (if abnormal pre-therapy), JAK2V617F allele burden (if JAK2V617F mutation present pre-therapy) after cycle 3,6,9,12 and then as determined appropriate by the investigator.
- Response assessment (IWG-MRT) monthly for first 3 cycles, then every 3 to 6 cycles
- Pregnancy test, urine or blood, (sensitivity of at least 50 mIU/mL) every week x 4, then every 4 weeks for all FCBP with regular menstrual cycles, or every 2 weeks if irregular cycles.
- Optional blood samples (20-50cc) on day 1 of cycle 2 for pharmacokinetics (PK) at approximately 0.5-1 hour, 2-4 hours, and 4-8 hours post ruxolitinib dose (3 time points). Not all research samples may be collected at all time points.
- Collect any unused study drug and review patient study drug dosing diary for compliance;
- Assessment of AEs using the NCI CTEP CTCAE, version 4.0 (published 28 May 2009)
- Myelofibrosis Symptom Assessment Form (MFSAF) questionnaire every cycle x3, then every 3 to 6 cycles
- MDASI (MD Anderson Symptom Inventory) questionnaire administration: patients will complete the paper or tablet PC version of the MDASI at every cycle x3, then every 3 to 6 cycles. Patients will be instructed in the use of an Interactive Voice Response (IVR) system that will be used to assess symptoms with the MDASI weekly for first 3 cycles of therapy when patients do not have clinic appointments. If patients do not respond to an IVR call, the research coordinator will attempt to personally contact the patient by telephone to complete the MDASI.

Outside Physician Participation During Treatment

- MDACC Physician communication with the outside physician is required prior to the patient returning to the local physician.
This will be documented in the patient record
- A letter to the local physician outlining the patient's participation in a clinical trial will request local physician agreement to supervise the patient's care (Appendix L)
- Protocol required evaluations outside MDACC will be documented by telephone, fax or e-mail. Fax and/or e-mail will be dated and signed by the MDACC physician, indicating that they have reviewed it.
- Changes in drug dose and/or schedule must be discussed with and approved by the MDACC physician investigator, or their representative prior to initiation, and will be documented in the patient record.
- A copy of the informed consent, protocol abstract, treatment schema and evaluation during treatment will be provided to the local physician.
- Documentation to be provided by the local physician will include drug administration records, progress notes, reports of protocol required laboratory and diagnostic studies and documentation of any hospitalizations.
- The home physician will be requested to report to the MDACC physician investigator all life threatening events within 24 hours of documented occurrence.
- Patients will return to MDACC every 2 weeks during Cycles 1 and 2, monthly for 2 cycles, then every 3 to 6 months as long as on the study for evaluation.

The patient will be contacted by the PI and his staff 30 days and 60 days after discontinuation of protocol +/-7 days to assess for AE's, unless the patient receives further cytotoxic chemotherapy treatment.

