7.0 REGULATORY AND REPORTING REQUIREMENTS

7.1 Serious Adverse Event Reporting (SAE) for M. D. Anderson-Sponsored IND Protocols

An adverse event or suspected adverse reaction is considered “serious” if, in the view of either the investigator or the sponsor, it results in any of the following outcomes:

- Death
- A life-threatening adverse drug experience – any adverse experience that places the patient, in the view of the initial reporter, at immediate risk of death from the adverse experience as it occurred. It does not include an adverse experience that, had it occurred in a more severe form, might have caused death.
- Inpatient hospitalization or prolongation of existing hospitalization
- A persistent or significant incapacity or substantial disruption of the ability to conduct normal life functions.
- A congenital anomaly/birth defect.

Important medical events that may not result in death, be life-threatening, or require hospitalization may be considered a serious adverse drug experience when, based upon appropriate medical judgment, they may jeopardize the patient or subject and may require medical or surgical intervention to prevent one of the outcomes listed in this definition. Examples of such medical events include allergic bronchospasm requiring intensive treatment in an emergency room or at home, blood dyscrasias or convulsions that do not result in inpatient hospitalization, or the development of drug dependency or drug abuse (21 CFR 312.32).

- Important medical events as defined above, may also be considered serious adverse events. Any important medical event can and should be reported as an SAE if deemed appropriate by the Principal Investigator or the IND Sponsor, IND Office.
- All events occurring during the conduct of a protocol and meeting the definition of a SAE must be reported to the IRB in accordance with the timeframes and procedures outlined in “The University of Texas M. D. Anderson Cancer Center Institutional Review Board Policy for Investigators on Reporting Unanticipated Adverse Events for Drugs and Devices”. Unless stated otherwise in the protocol, all SAEs, expected or unexpected, must be reported to the IND Office, regardless of attribution (within 5 working days of knowledge of the event).

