7.2 Expedited reporting by investigator to Incyte and Celgene

Serious adverse events (SAE) are defined above. The investigator will inform Incyte and/or Celgene of any SAE within 24 hours of being aware of the event via email and/or fax. Respective companies will be informed based on the attribution of a given SAE:

1. Due to INCB018424 alone – These SAEs will only be reported to INCYTE.
2. Due to the Lenalidomide – These SAEs will only be reported to CELGENE.
3. Due to both the INDB018424 and the Lenalidomide – These SAEs will be reported to INCYTE and CELGENE.
4. All pregnancies will be reported to both companies.

If the investigator can't associate causality with one or the other alone then causality needs to be associated with the combination of the products. These SAEs will go to both INCYTE and CELGENE.

Adverse events will be documented in the medical record and entered into the case report form. PDMS/ CORE will be used as the electronic case report form for this protocol. Investigator or physician designee is responsible for verifying and providing source documentation for all adverse events and assigning the attribution for each event for all subjects enrolled on the trial. SAEs must be documented on MDACC "Internal SAE Report Form for Prompt Reporting". This form must be completed and supplied to Incyte and/or Celgene within 24 hours/1 business day at the latest on the following working day. The initial report must be as complete as possible, including details of the current illness and (serious) adverse event, and an assessment of the causal relationship between the event and the investigational product(s). Information not available at the time of the initial report (e.g., an end date for the adverse event or laboratory values received after the report) must be documented on a follow-up MDACC SAE reporting form.

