This phase II clinical trial will have a stopping rule based on toxicity defined as an adverse events considered to be at least possibly related to treatment. In particular, accrual to the study will be temporarily suspended if: a) 2 or more among the first 10 subjects treated on this trial experiences a Grade 4 non-hematologic toxicity or a

serious adverse event that is felt to be drug related. b) 20% or more of subjects (when more than 10 subjects have been accrued) experience a Grade 4 non-hematologic toxicity or serious adverse event that is felt to be drug related. After consideration by the study team (study chair, statistician), a decision will be made as to whether accrual can resumed after approval of the appropriate IRB.

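### The home physician's 24-hour reporting request covers only life-threatening events, narrower than the drug-related SAEs and Grade 4 non-hematologic toxicities that drive the accrual pause, so some countable events may reach the center weeks late

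*Combined protocol and SAP*

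**What the plan says.** **Local reporting.** Under Outside Physician Participation in Section 5.6: "The home physician will be requested to report to the MDACC physician investigator all life threatening events within 24 hours of documented occurrence". The same list asks for "progress notes, reports of protocol required laboratory and diagnostic studies and documentation of any hospitalizations", with no time limit.

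**What counts as serious.** Section 7.1 lists "Inpatient hospitalization or prolongation of existing hospitalization" as a seriousness criterion of its own, separate from the life-threatening criterion, which it limits to immediate risk of death.

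**What pauses accrual.** Section 8.0 suspends accrual if "2 or more among the first 10 subjects treated on this trial experiences a Grade 4 non-hematologic toxicity or a" drug-related SAE. After that it suspends accrual if "20% or more of subjects (when more than 10 subjects have been accrued) experience a Grade 4 non-hematologic toxicity or serious adverse event" judged drug related. Neither limb is confined to life-threatening events.

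**When the clocks start.** Section 7.1 says SAEs "must be reported to the IND Office, regardless of attribution (within 5 working days of knowledge of the event". Section 7.2 says "The investigator will inform Incyte and/or Celgene of any SAE within 24 hours of being aware of the event via email and/or fax". Both run from the center's knowledge. Section 7.2 also makes the investigator or a physician designee responsible for attribution.

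**The concern.** A pausing rule works only on the events known when it is checked. Here the trigger for prompt local reporting is narrower than the set of events the rule counts. A patient may be admitted near home with a non-life-threatening event that the investigator would call at least possibly related. In the text supplied, no one outside the center has a deadline for reporting it. Until the center hears, attribution cannot be assigned, the event is not in the count, and the reporting clocks have not started. No clause is breached meanwhile, so monitoring for protocol compliance would not reveal the gap. At stake is whether patients continue to be enrolled for some weeks after the true count has reached the level set for suspension.

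**Working it through.** The plan states no operating characteristics for the pausing rule, so there is no figure of its own to reproduce on this point. The Simon design figures in Section 8.0 do reproduce (exact alpha 0.0966, power 0.8012, early termination under the null 0.455 against the stated 46%) and are unaffected.

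**1. Events covered**

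| Event | Timed local report (5.6) | Counts toward pause (8.0) |
|---|---|---|
| Life-threatening, drug related | Yes, 24 hours | Yes |
| Hospitalization, not life-threatening, drug related | No | Yes |
| Other SAE category, not life-threatening, drug related | No | Yes |
| Grade 4 non-hematologic, drug related | Only if also life-threatening | Yes |

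For the last row, Section 8.0 grades by CTCAE while Section 7.1 tests for immediate risk of death. Meeting one does not guarantee meeting the other.

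**2. Routine contact intervals**

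Section 5.6 brings patients to the center every 2 weeks in cycles 1 and 2, monthly for 2 cycles, then every 3 to 6 months. Footnote 9 of Appendix I adds local visits at least every 28 days with study-staff phone contact, and a window of 7 days either way.

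- Cycles 1 and 2: 14 days; 14 + 7 = 21 days with one window.
- Afterwards: 28 days; 28 + 7 = 35 days with one window; 28 + 7 + 7 = 42 days if one contact is a week early and the next a week late.

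**3. Sensitivity of the count**

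After subject 10 the threshold is 0.20 × n, rounded up. The rule is therefore met at 2 of 10, 3 of 11, 4 of 20, 7 of 31 and 10 of 49. One late event changes the decision only when the true count equals the threshold, for example exactly 2 among the first 10.

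As an outer bound, let p be an assumed true rate of qualifying events per subject and s the share known when the rule is checked, with q = p × s. Then P(2 or more in 10) = 1 − (1 − q)^10 − 10q(1 − q)^9. With p = 0.20:

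- s = 1, q = 0.20: 62%
- s = 0.75, q = 0.15: 46%
- s = 0.50, q = 0.10: 26%

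This treats unknown events as never counted, so it overstates the effect of a delay. Neither p nor s is in the documents.

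**4. Patients enrolled during the delay**

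The documents give no accrual rate. Assume 2 to 4 patients per month of 30.4 days.

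- Early: 14/30.4 × 2 = 0.9 to 21/30.4 × 4 = 2.8, about 1 to 3 patients.
- Later: 28/30.4 × 2 = 1.8 to 42/30.4 × 4 = 5.5, about 2 to 6 patients.

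**The case against.** The strongest reply is that other clauses bring most of these events to the center quickly.

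- Section 5.6 requires center approval before any change in dose or schedule, and Section 5.1 makes interruption mandatory for drug-related Grade 3 or 4 non-hematologic toxicity. Together they should prompt a call for most of the serious related events the pause counts.
- In cycles 1 and 2, when the first-10 check is most likely to matter, there are 2-weekly center visits and weekly blood tests. Weekly symptom calls run through cycle 3, with coordinator follow-up if the patient does not answer.
- Local evaluations are sent to the center, and hospitalization records must be provided.
- Section 7.1 holds the investigator and research team responsible for SAE reporting.

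Most of this stands, and it limits the point considerably. It does not close the gap. The approval and interruption clauses operate locally only if the event is thought drug related and a dose is to change. An admission that the local physician calls unrelated, but the investigator would call possibly related, prompts no such contact. The symptom calls collect a symptom inventory, not SAEs. Footnote 9 does not say what the 28-day call covers, although it states an adverse-event purpose for the post-discontinuation contacts. Hospitalization records carry no deadline.

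A reader might also infer stronger versions, which the documents do not support:

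- **That the pause counts every SAE.** It counts drug-related SAEs and Grade 4 non-hematologic toxicities. Only the reporting clauses cover all SAEs.
- **That events stay hidden for 84 to 168 days while up to 22 patients enter (168/30.4 × 4).** This needs every backstop to fail. The sparse-visit period also begins only after about 4 cycles (112 days). At 4 per month about 15 patients would then be enrolled, leaving about 16 before the hold at 31, and stage 2 adds only 18.
- **That the 24-hour company report would be breached.** Its clock starts at awareness, so the report is late relative to the event but compliant.
- **That events are lost.** They are delayed, provided the records arrive.

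**Conclusion.** The mismatch is real and can be read directly from Sections 5.6, 7.1, 7.2 and 8.0 without any assumed figure. Its reach is limited to non-life-threatening SAEs that are judged unrelated locally or lead to no dose change, and that the investigator would attribute at least possibly to treatment. For these, counting may lag by about 2 to 3 weeks in cycles 1 and 2 and about 4 to 5 weeks afterwards, with 42 days as the extreme. The delay figures assume that the next routine contact reveals the event. The patient counts (about 1 to 3 early, about 2 to 6 later) rest on the assumed accrual rate and matter only when the count is at the threshold. The Appendix L letter and the Appendix C reporting guidelines are not in the supplied text; if either already sets a local deadline for all SAEs, the point reduces to aligning Section 5.6 with it. Sample size and efficacy decision rules are unaffected.

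**What to change.** In Section 5.6, change the scope of the home physician's 24-hour request from life-threatening events to *all serious adverse events as defined in Section 7.1, regardless of attribution, and all Grade 4 non-hematologic toxicities*. Keep the same 24 hours from documented occurrence. Including events regardless of attribution matters because Section 7.2 leaves that judgment to the investigator or designee. Conform the Appendix L letter if it uses the narrower wording.

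The cost is one sentence in the protocol, possibly one in the letter, and a few more calls from local offices. No dose rule, eligibility criterion, endpoint or pause threshold changes.

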5.7 Criteria for Removal from the Study

Treatment with study drugs is to be discontinued when any of the following occurs:

- Lack of therapeutic effect (any effort should be made to provide therapy to the patient in a safe way for at least 3-6 cycles for proper assessment of potential efficacy)
- Adverse event(s) that, in the judgment of the Investigator, may cause severe or permanent harm or which rule out continuation of study drug.
- Withdrawal of consent
- Lost to follow up
- Death
- Suspected pregnancy

6.0 CRITERIA FOR RESPONSE

Best overall response will be categorized according to the International Working Group Criteria:

Complete remission (CR): Requires all of the following in the absence of both transfusion and growth factor support;

- Complete resolution of disease-related symptoms and signs including palpable hepatosplenomegaly.
- Peripheral blood count remission defined as hemoglobin > 11 g/dL, platelet count $\geq 100 \times 10^9/L$, and absolute neutrophil count $\geq 1.0 \times 10^9/L$.
- Normal leukocyte differential including disappearance of nucleated red blood cells and immature myeloid cells in the peripheral smear, in the absence of splenectomy.*
- Bone marrow histological remission defined as the presence of age-adjusted normocellularity, < 5% myeloblasts, and an osteomyelofibrosis grade of ≤ 1 .**

Partial remission (PR): Requires all of the above criteria for CR except the requirement for bone marrow histological remission. However, a repeat bone marrow biopsy is required in the assessment of PR and may or may not show favorable changes that do not however fulfill criteria for CR.

Clinical improvement (CI): Requires one of the following in the absence of both disease progression (as outlined below) and CR/PR assignment (*CI response is validated only if it lasts for ≥ 8 weeks*).

- A ≥ 2 g/dL increase in hemoglobin level or becoming transfusion independent (applicable only for patients with baseline hemoglobin level of < 10 g/dL).[§]
- Either a $\geq 50\%$ reduction in palpable splenomegaly of a spleen that is ≥ 10 cm at baseline or a spleen that is palpable at > 5 cm at baseline becomes not palpable.^{§§}
- A $\geq 100\%$ increase in platelet count and an absolute platelet count of $\geq 50,000 \times 10^9/L$. (applicable only for patients with baseline platelet count of < $50 \times 10^9/L$).
- A $\geq 100\%$ increase in ANC and an ANC of $\geq 0.5 \times 10^9/L$ (applicable only for patients with baseline absolute neutrophil count of < $1 \times 10^9/L$).

Progressive disease: Requires one of the following:[¶]

- Progressive splenomegaly that is defined by the appearance of a previously absent splenomegaly that is palpable at > 5 cm below the left costal margin or a $\geq 100\%$ increase in palpable distance for baseline splenomegaly of 5-10 cm or a $\geq 50\%$ increase in palpable distance for baseline splenomegaly of > 10 cm.
- Leukemic transformation confirmed by a bone marrow blast count of $\geq 20\%$.
- An increase in peripheral blood blast percentage of $\geq 20\%$ that lasts for ≥ 8 weeks.

Stable disease: None of the above.

Relapse: Loss CR, PR, and CI. In other words, a patient with CR or PR is considered to have undergone relapse when he or she no longer fulfills the criteria for CI.

**Because of subjectivity in peripheral blood smear interpretation, CR does not require absence of morphological abnormalities of red cells, platelets, and neutrophils.*

*** In patients with CR, a complete cytogenetic response is defined as failure to detect a cytogenetic abnormality in cases with a pre-existing abnormality. A partial cytogenetic response is defined as 50% or greater reduction in abnormal metaphases. In both cases, at least 20 bone marrow- or peripheral blood-derived metaphases should be analyzed. A major molecular response is defined as the absence of a specific disease-associated mutation in peripheral blood granulocytes of previously positive cases. In the absence of a cytogenetic/molecular marker, monitoring for treatment-induced inhibition of endogenous myeloid colony formation is encouraged. §Transfusion dependency is defined by a history of at least 2 units of red blood cell transfusions in the last month for hemoglobin of < 8.5 g/dL that was not associated with clinically overt bleeding. Similarly, during protocol therapy, transfusions for hemoglobin of ≥ 8.5 g/dL is discouraged unless it is clinically indicated.*

§§In splenectomized patients, palpable hepatomegaly is substituted with the same measurements.

¶It is acknowledged that worsening cytopenia might represent progressive disease but its inclusion as a formal criterion was avoided because of the difficulty distinguishing disease-associated from drug-induced myelosuppression. However, a decrease in hemoglobin of ≥ 2 g/dL, a 100% increase in transfusion requirement, and new development of transfusion dependency, each lasting for more than 3 months after the discontinuation of protocol therapy can be considered disease progression.

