8.0 STATISTICAL CONSIDERATIONS

All subjects meeting the eligibility criteria that have signed a consent form and have begun treatment will be evaluable for response. This is a two stage, phase II trial designed to assess the effect of therapy in subjects with Primary, Post Polycythemia Vera, or Post Essential Thrombocythemia Myelofibrosis (PMF, post-PV MF, or post-ET MF). Secondary objective is to determine the safety of therapy in this population.

The primary objective of this study is to assess efficacy in terms of the objective response rate (complete and partial response, and clinical improvement by IWG-MRT) in patients with MF. The Min-Max two-stage design proposed by Simon will be implemented. Sample size and decision criteria are chosen to reduce the expected accrual if the treatment is ineffective in regard to response relative to having no interim stopping rule. The target response rate is 50%. A response rate of 35% or less will be considered unacceptable and treatment with the therapy will be discontinued. Given the response rates stated above, if the probability of inappropriately accepting a poor therapy is 10% ($\alpha=0.1$), a total sample size of 49 patients will result in 80% power ($\beta=0.2$).

In the first stage of the design, a total of 31 patients will be enrolled and the study will be put on hold to assess response. If 10 or fewer patients respond to the combination therapy, after being treated for 6 months or discontinued due to excessive toxicity or lack of efficacy, then the study will be terminated and the therapy will be declared ineffective. Those patients who stopped receiving one of the two study drugs due to safety reasons will be counted as failures in the efficacy analysis. However, if 11 or more patients respond, up to an additional 18 patients will be enrolled to complete the study.

After a total of 49 patients have been enrolled into the study, if 21 or fewer patients respond to the therapy, the therapy will be declared ineffective. However, if greater than 21 patients respond to the therapy, the therapy will be considered efficacious. The probability of early termination due to unacceptable response rate is 46% under the null hypothesis.

Data from all subjects who receive any study drug will be included in the safety analyses. Subjects who entered the study and did not take any of the study drug and had this confirmed, will not be evaluated for safety.

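### The 2 g/dL hemoglobin limb of clinical improvement has no transfusion-free condition, so a rise sustained by transfusion can count as a primary-endpoint response; the exposure is narrow

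*Combined protocol and SAP*

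**What the plan says.** The primary endpoint in Section 8.0 is the "objective response rate (complete and partial response, and clinical improvement by IWG-MRT) in patients with MF", so a CI has the same weight as a CR or PR at both decision points (11 of 31 to continue, 22 of 49 to declare efficacy).

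Section 6.0 treats transfusion differently across the three categories:

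- **CR** must occur "in the absence of both transfusion and growth factor support".
- **PR** inherits this: "Requires all of the above criteria for CR except the requirement for bone marrow histological remission".
- **CI** has the header "Requires one of the following in the absence of both disease progression (as outlined below) and CR/PR assignment", plus a duration of at least 8 weeks. Transfusion is not mentioned. The hemoglobin bullet is a 2 g/dL or greater "increase in hemoglobin level or becoming transfusion independent (applicable only for patients with baseline hemoglobin level of" less than 10 g/dL.

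The footnote to that bullet defines transfusion dependency (at least 2 red cell units in the last month for hemoglobin below 8.5 g/dL, not tied to overt bleeding). It also advises against on-study transfusion at 8.5 g/dL or more unless there is a clinical reason. It does not say how to score a transfused patient.

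Section 5.3 states: "Packed red blood cell or platelet transfusions are allowed when necessary". The progression footnote in Section 6.0 covers a hemoglobin fall, a doubled transfusion requirement and new dependency, but only "each lasting for more than 3 months after the discontinuation of protocol therapy can be considered disease progression".

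The exploratory anemia analysis in Section 8.0 does restrict the 2 g/dL rise to transfusion-independent patients who need no transfusion during the study. It reports transfusion-dependent patients separately.

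**The concern.** The two limbs of the hemoglobin bullet are joined by *or*. The second, becoming transfusion independent, therefore places no restriction on the first. A patient whose hemoglobin stays at least 2 g/dL above baseline because of red cell transfusion meets the wording of the first limb. The absence-of-progression condition does not remove that patient, because transfusion need during treatment is not progression under the footnote.

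The trial is single-arm and its conclusion rests on a count of responders. A supportive measure the protocol allows could add to that count without any drug effect. The exploratory anemia measure is, on this point, stricter than the endpoint that decides the trial.

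**Working it through.** **1. The plan's design reproduces.** Inputs from Section 8.0: unacceptable rate 35%, target 50%, 31 patients in stage 1 (stop at 10 or fewer responders), 49 in total (ineffective at 21 or fewer). With X₁ ~ Bin(31, p) and X₂ ~ Bin(18, p):

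- P(stop early) = P(X₁ ≤ 10)
- P(declare efficacy) = Σ over x = 11 to 31 of P(X₁ = x) · P(X₂ ≥ 22 − x)

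At p = 0.35, P(stop early) = 45.5% (stated 46%) and P(declare efficacy) = 9.66% (limit 10%). At p = 0.50, power = 80.1% (stated 80%). The design figures are sound; the issue is who counts as a responder.

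**2. Who can reach the rise limb through transfusion.** The limb needs baseline + 2 g/dL, lasting 8 weeks. Suppose transfusion is given only when hemoglobin falls below 8.5 g/dL, as the footnote advises. The reading just before transfusion is then just under 8.5.

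| Baseline (g/dL) | Level needed (g/dL) | Needed minus 8.5 | Held throughout if transfused only below 8.5? |
|---|---|---|---|
| 6.5 | 8.5 | 0.0 | Borderline |
| 7.0 | 9.0 | +0.5 | No |
| 7.5 | 9.5 | +1.0 | No |
| 8.0 | 10.0 | +1.5 | No |

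A patient managed within that advice keeps the rise throughout only if baseline is about 6.5 g/dL or lower. At higher baselines, one of two things is needed:

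- transfusion at 8.5 g/dL or more for a clinical reason, which is discouraged but allowed; or
- CI judged only at readings taken soon after transfusion. Section 5.6 schedules blood counts weekly for 2 cycles and then every 2 weeks, but response assessment monthly for 3 cycles and then every 3 to 6 cycles. Section 6.0 does not say which readings establish the 8 weeks.

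**3. Illustration of size.** The documents give no misclassification rate, so the share m of true non-responders scored as CI through transfusion is assumed. With a true rate of 35%, the apparent rate is q = 0.35 + 0.65m, and the design is re-evaluated at q. Expected misclassified patients in 49 = 49 × 0.65 × m.

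| m (assumed) | q | Expected misclassified in 49 | P(declare efficacy) |
|---|---|---|---|
| 0 | 35.0% | 0 | 9.7% |
| 0.5% | 35.3% | 0.16 | 10.5% |
| 1% | 35.7% | 0.32 | 11.4% |
| 3% | 37.0% | 0.96 | 15.6% |
| 5% | 38.3% | 1.59 | 20.6% |

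This takes 35% as a rate free of transfusion artefact.

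**The case against.** The strongest reply is that the footnote on this same bullet removes most of the problem. It advises against transfusion at 8.5 g/dL or more, and step 2 shows that a patient managed within that advice rarely holds a 2 g/dL rise for 8 weeks. This stands, and it limits the point to the three routes named. It does not close the gap, because it is advice on giving blood with an exception, and not a scoring rule.

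A reader might infer something stronger: that patients made transfusion dependent by study drug would commonly be scored as responders, or that the error rate is well above 10%. The documents do not support either. Dependency under Section 6.0 means transfusion for hemoglobin below 8.5 g/dL, which is hard to combine with a sustained 2 g/dL rise unless baseline is very low. The anemia frequencies in Section 2.1 (50% to 70% anemic, 25% below 8.0 g/dL) describe myelofibrosis at diagnosis, and they do not measure the exposed group.

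Two further replies have force. The 35% reference rate is not derived in the plan; if it reflects results scored under the same criteria, the comparison may be like for like and no inflation follows. Also, the plan names the International Working Group criteria, so adding a condition modifies a named standard. Both are reasons to report the unmodified rate as well. Finally, the exploratory anemia summaries would make some transfusion-driven rises visible, but they do not alter the primary count.

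**Conclusion.** The gap is real on the text. CR, PR and the exploratory anemia outcome all exclude transfusion support, while the 2 g/dL limb of CI does not, and no other rule in the plan supplies the condition. The group affected is narrow, and its size cannot be derived from the documents. The range of 10.5% to 20.6% against 9.7% rests on assumed misclassification of 0.5% to 5% of true non-responders and on 35% being free of transfusion artefact. It shows sensitivity and is not an estimate: about one expected misclassified patient in 49 (m = 3%) corresponds to 15.6%. Sample size and boundaries need no change. Severity: should-fix, because the exposure is limited but the endpoint is primary and the remedy is small.

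**What to change.** Amend the scoring rule in Section 6.0, with no change to patient care:

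- For the primary endpoint, count the 2 g/dL limb only in patients who are not transfusion dependent at baseline and who receive no red cell transfusion during the 8-week validation period. Transfusion for overt bleeding may be handled separately, as the dependency footnote already does.
- Let transfusion-dependent patients qualify on hemoglobin only by becoming transfusion independent.
- Define transfusion independence in Section 6.0, where it is currently undefined, consistently with Section 8.0 (12 weeks without red cells). Reconcile the two definitions of dependency: one month in Section 6.0, three months in Section 8.0.
- Report the response rate under the unmodified criteria alongside.

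The cost is a few sentences, the matching programming rule, a possibly slightly lower observed response rate, and a small stated modification of the named criteria. Transfusion history is already collected (Sections 5.5 and 5.6, Appendix I). One check is needed: after cycle 3, visits are 3 to 6 cycles apart while Section 5.6 asks for transfusions in the previous cycle, so the history used for scoring should cover the whole validation period.
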